12. SAFETY MONITORING

The study will monitor participant safety. One aspect of safety monitoring is to evaluate potential study participants at screening to determine whether it is safe for them to participate in the interventions. This will be done in collaboration with the participant's PCP, who will have received information and training about the trial, particularly its eligibility criteria, interventions, and safety monitoring procedures. In this trial, primary care will be provided by the participant's PCP, not by study personnel. A second aspect is monitoring the safety of enrolled participants. If a participant develops a medical problem, the safety of continuing or resuming the intervention will be ascertained by the participant's PCP in collaboration with a study clinician. The

Patterned after protocol published online in association with Appel et al. (2011)¹⁵

investigators met weekly during the active intervention phase with the community health workers/ change agents to discuss, among other things, evidence of adverse events. Surveillance for serious adverse events and other relevant clinical events occurred as needed. Third, if we became aware of medical problems from abnormal physical measurements, such as blood pressure assessment, we referred the patient to her primary care physician and follow-up to make sure that she completed the referral. Results of routine physical measures obtained as part of study visits will be provided to the participant's PCP with patient's consent. In addition, the staff were prepared to address immediately items meeting the criteria for 'Alert Values' listed in the table below. A designated study clinician with appropriate expertise will be designated as the 'Health Safety Officer' and will review medical eligibility criteria and clinical measures as needed. The Safety Officer will also be responsible for reviewing and reporting SAEs for the site, as detailed elsewhere. This person or persons will have appropriate back-up during vacations or other absences to provide 24/7 medical safety coverage for the duration of the study.

Potential Risks

The following sections describe potential risks associated with the study along with procedures to minimize risk.

Physical Activity

We recognize the need to minimize the potential risks of physical activity in previously sedentary individuals with CVD risk factors. During the screening process, we will exclude persons with a CVD event within the past 6 months. In screenees with a prior CVD event (over 6 months ago), diabetes, peripheral vascular disease, or a positive Rose Angina Questionnaire, PCP approval is required specific to the patient's CVD risk. In order to protect the participants' safety, we will continuously reinforce our recommendation to engage in moderate-intensity physical activity. We will also recommend a safety evaluation by their PCP for those participants who wish to progress to vigorous physical activity. Still, it is important to acknowledge the participant's autonomy. We can recommend that participants follow safety advice but cannot force them to do so.

Nutrient Intake

Calorie restriction can theoretically lead to inadequate nutrition or excessive, rapid weight loss. To minimize these risks, participants are encouraged to eat a variety of foods from all food groups and to maintain an adequate calorie level. 6 month follow-up to check that patients are not suffering excessive weight loss. Participants will be advised that marked and sustained caloric restriction can have serious health risks, e.g. gallstones and/or cholecystitis.

Hypoglycemia Related to Exercise and Lifestyle Interventions

For patients who may be susceptible to hypoglycemia due to use of anti-diabetic medications, weight loss interventions have the potential to increase the risk of hypoglycemia, especially during the time when diet and/or physical activity interventions are implemented. To minimize the risk of hypoglycemia, we will require PCP approval prior to enrolling individuals with diabetes. PCPs are provided with relevant information, prepared by the study clinicians. In addition, participants are educated about symptoms of hypoglycemia. They are urged to contact their PCP if they have symptoms or blood glucose values suggestive of hypoglycemia. Changes in diabetic regimens and overall management of diabetes remain under the control of the participant's PCP.

Symptomatic Hypotension Related to Exercise and Lifestyle Interventions

Patterned after protocol published online in association with Appel et al. (2011)¹⁵

For patients who may be susceptible to hypotension because they are using medications that lower blood pressure, weight loss interventions have the potential to increase the risk of hypotension. Participants are educated about symptoms of hypotension and urged to contact their PCP if they have symptoms suggestive of hypotension. In addition, staff contact will notify PCP of participants who develop symptomatic hypotension while on anti-hypertensive medications. Changes in blood pressure regimens and overall management of hypertension remain under the control of the participant's PCP.

Cardiovascular Events

All participants with cardiovascular disease (CVD) require approval from their PCP prior to enrolling. PCPs are provided with information about safety guidelines for physical activity for people with CVD. In addition, participants are educated about CVD symptoms and urged to contact their PCP if they have a change in their CVD symptoms. Overall CVD management remains under the control of the participant's PCP. Cardiovascular events are also assessed using a standardized questionnaire at regular, pre-specified intervals. When a staff member learns that a cardiovascular event (including a procedure) has occurred, the physical activity component of the intervention is suspended. The intervention may be resumed after approval from the participant's PCP.

Alert Values

Table 8 lists the alert values and subsequent actions that will occur. In general, the participant, safety officer, and PCP will be notified.

Table 9. Alert Values and Actions

Measure	Alert Value	Notify participant
Blood pressure (avg.)	Level 1 SBP \geq 180mm/Hg OR DBP \geq 110mm/Hg	In clinic. Advise to follow-up with PCP within 1 week
	Level 2 SBP \geq 140mm/Hg OR DBP \geq 90mm/Hg	In clinic. Advise to follow-up with PCP within 1 month.
	Level 3 SBP \leq 70mm/Hg OR DBP \leq 50mm/Hg	In clinic. Advise to follow-up with PCP within 2 months.
PHQ-9 (Depression questionnaire)	Total score \geq 16 & $<$ 21	In clinic. Advise to follow-up with PCP or mental health care provider within 1 month.
	Total score \geq 21	In clinic. Advise to follow-up with PCP or mental health care provider within 1 week

Surveillance and Reporting Procedures

Serious Adverse Events (SAE)

As defined by the Food and Drug Administration, serious adverse events include the following:

- death,
- a life-threatening experience,

Patterned after protocol published online in association with Appel et al. (2011)¹⁵

- inpatient hospitalization or prolongation of existing hospitalization,
- a persistent or significant disability/incapacity, or
- a congenital anomaly/birth defect.

Important medical events that do not result in death or require hospitalization may be considered serious adverse events if they jeopardize the participant's health or require medical or surgical intervention to prevent one of the outcomes in the definition. Surveillance for serious adverse events and other relevant clinical events that may be associated with study participation will occur at in-person visits scheduled at 6 months and 12 months after randomization. This is done using a standardized questionnaire. In addition to the fixed time points, participants may report events in other settings, e.g. phone and intervention contacts. These events will be referred to unmasked staff that will gather relevant information and complete the standardized questionnaire. A study clinician will review the completed forms, will classify the event according to several dimensions (expectedness, relatedness, and type), and will take appropriate action. Safety-related events will be reported in a timely fashion as required by the Safety officer, the IRB, and PCORI.

Expected Events

Over the duration of the trial, which could last up to six months, a number of medical events may be expected to occur in obese adults, including routine surgeries and procedures, the development of cancer or other chronic conditions, increased symptoms from a chronic condition, musculoskeletal problems, motor vehicle accidents, and other types of accidents (e.g. falls, acts of violence).

Pregnancy and Other Exclusions

If a participant becomes pregnant during study after enrollment she is then excluded. If a participant develops cancer, unstable angina, or another condition for which weight loss or exercise might be contraindicated, further participation will be determined by the participant's PCP in conjunction with a study clinician.

Data Safety and Monitoring Plan

The data safety and monitoring plan for this study should be proportional to the degree of risks of the trial. We believe that this study has minimal risk based on our prior studies in this area. We therefore will not have a data safety and monitoring board for this study. However, based on our prior studies, we will conduct regular and thorough monitoring of the data by the PIs, project manager and director, and statistician, and lead research assistants. The PIs and study team will meet weekly to review recruitment, enrollment, retention, adverse events, and adherence to study protocols for data collection, and data storage. Cases will be reviewed for any issues related to privacy or confidentiality or potential cases of child abuse, victimization, or psychological distress. Patients will be provided with contact information for the project manager/director/PIs if questions arise. The IRB and PCORI will be informed if any patient experiences a serious adverse event or if the patient has concerns about the study. Staff will be fully trained to be able to address serious adverse events. The team will undergo human subjects protection training via the CITI modules of "Social & Behavioral Researchers & Staff" and HIPPA training.

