5. STUDY POPULATION

Study population. This population is primarily working poor families who would have to choose between food and medication were it not for TCC's services. Approximately 98% of TCC's patients are under 200% of the Federal Poverty Level. About 44% of TCC's patients are uninsured, and that number has been increasing. The ethnic composition of TCC's patient population is 76% Latino, 13% African American, 4% Asian, 4% White, 1% American Indian, less than 1% Alaskan Native, Native Hawaiian or Pacific Islander, and 2% Other. About 58% of patients are female, 42% are male; 66% are children, while 34% are adults. With nearly 100,000 patient visits in the last year and 8 clinics, TCC has more than enough obese adult patients (N ~2,000) to yield the number that the investigators plan to enroll in the proposed intervention trial. To ensure maximum range of patient participation, recruitment involved two clinic sites. These sites are located in Long Beach, California. General information about each medical practice and its providers, as well as specific information about weight loss management strategies, will be collected at baseline and during follow-up. The UCLA investigators are familiar with strategies for recruiting participants from the clinic waiting room in TCC clinics by virtue of having used these strategies as part of a predecessor NIH-funded intervention study.

6. ELIGIBILITY TO PARTICIPATE IN THE STUDY.

To optimize the internal validity of this study and minimize potential risks for individuals for whom participation would not be appropriate, the following eligibility criteria were developed:

Table 1 Eligibility Criteria
Inclusion Criteria

- BMI ≥ 27 & BMI $<40.4 \text{ kg/m}^2$ [had been BMI ≥ 30 & BMI <40]² and weight $\leq 400 \text{ lbs. if observed}$
- Age ≥ 18 years
- Willingness to change diet, physical activity and weight
- Willing to accept randomization to each group
- Able to give informed consent

² Knowing that accrual could be challenging, from the outset participants whose BMI fell short of the lower limit of 30 were told that there was a chance that they might be eligible later. When accrual was determined to be slower than planned, with IRB approval the range was extended to those with a BMI ≥ 27 .

Patterned after protocol published online in association with Appel et al. (2011)¹⁵

- Persons with the following conditions are eligible with PCP approval:
 - i) Diabetes Mellitus
 - ii) Prior CVD event > 6 months

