8. DATA COLLECTION AND MEASUREMENTS

Data Collection Assessment Periods

Eligibility, baseline and follow-up data will be collected by phone and at in-person visits in the home or in the clinic site waiting room. Intervention process data will be collected separately. In-person data collection visits will be conducted in the waiting rooms of the participating clinics. The following contacts describe the primary data collection points for participant level data.

Prescreen Contacts: During the initial waiting room contact, research staff will provide information about the trial and will collect additional data on eligibility. Those who remain interested and eligible will be consented to participate in the screening phase and will begin to complete screening visit measures. Most patients will complete screening and enrollment activities in this initial visit, some will finish the self-report data assessment but many will be

Patterned after protocol published online in association with Appel et al. (2011)¹⁵

called up for their appointment and therefore will have to leave off completion of the self-report data assessment at a later time. The study participant will be scheduled for an in-person screening visit and will be provided a number to call if interested in asking additional questions.

Screening Visit: Interested persons who are unable to complete screening and enrollment procedures during their first contact will be scheduled at their TCC clinic site from which they were recruited, where their blood pressure, waist circumference, height and weight will be measured. If these measures indicate continued eligibility then the participant will be provided more detail about the trial. Written informed consent to participate in the full trial will be obtained. After consent has been signed, the patient will be randomized and questionnaire data be collected.

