Randomization procedure. If all screening and baseline measures indicate that the patient remains eligible, a programmed application in REDCap generates a random assignment to experimental condition for the patient at the end of the screening assessment. The lifestyle change coaches can look up in REDCap's database the study participants assigned to their condition. The coach will then call the patient and arrange for the first coaching session, if appropriate. The research assistants will be kept ignorant of the patient's assignment to experimental condition, to reduce the chance for bias. Of necessity, the lifestyle change coaches will be aware of the patient's experimental assignment but will be instructed to follow the protocol carefully, so as not to introduce any personal bias.

The REDCap data entry system has also been programmed to generate a randomly determined assignment to condition, if the would-be participant met all inclusion criteria and reported no exclusion criteria. Hence, at the completion of the screening visit the study participant will be informed about the experimental condition that he/she had been assigned to and the name and contact number of his/her lifestyle coach. More information about the randomization process is provided below.

Follow-Up (FU) Visits: Participants will be asked to attend in-person follow-up visits at 6 and 12 months after randomization. Most of these data will be collected in-person at the clinic but the FFQ may be administered over the phone, depending on the time constraints of the study participant. The target windows used to schedule participants will coincide with a one month period around the 6 and 12 months follow-up visits. During follow-ups, we will also ask patients to evaluate the trial, including their perceptions of the acceptability and usefulness of the intervention and its components (MyPlate or Calorie Counting).

Measurement intervals.

Most measures will be assessed at baseline, at 6 months and 12 months follow-up. The Block Food Frequency Questionnaires will be administered only at baseline and 12-months follow-up, not at 6-months follow-up, to minimize the burden on study participants. Questionnaires were administered in the order described below in Table 4.

Table 4: Data Collection Items and Schedule by Contact

	Screening	Baseline	F-up-6	F-up-12
Eligibility/Interest	X			
Informed Consent	X	X		
Weight (self-reported)	X			
Height (self-reported)	X			
Weight (measured)		X	X	X

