Height (measured)		X	X	X
Waist (measured)		X	X	X
BP (measured)		X	X	X

Patterned after protocol published online in association with Appel et al. (2011)¹⁵

Randomization		X		
Questionnaire topics (administered in this order)				
Demographics/Medical	X	X		X
WHO Health and performance questionnaire		X	X	X
Health-Related QoL-SF-12		X	X	X
Mental Health Inventory (MHI-5)		X	X	X
Physical Activity Quest. (IPAQ)		X	X	X
Physical Activity self-efficacy		X	X	X
Outcomes: hunger – fullness - satisfaction		X	X	X
MyPlate adherence		X	X	X
MyPlate self-efficacy		X	X	X
Weight loss history		X	X	X
Weight control self-efficacy (WEL-SF)		X	X	X
Patient sense of autonomy		X	X	X
Patient satisfaction with care			X	X
Social support and eating habits survey		X	X	X
Social support and exercise survey		X	X	X
TV/Monitor use time		X	X	X
USDA Short-Form Food Security survey		X	X	X
Medical History survey			X	X
Patient satisfaction with weight loss program			X	X
Block Food Freq. Quest.		X		X

*note. F-up-6 = follow-up assessment 6 months after randomization; F-up-12 =follow-up assessment 12 months after randomization.

Principal Measures

The following sections describe the specific measurements to be collected from participants at each contact point in the trial. After considering the total burden of data collection procedures and measurements, we may drop or modify some items. We may also add questionnaires. For example, to improve study procedures and interventions, we will query participants about their experiences in the study.

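### Section 12 makes a positive Rose Angina Questionnaire a trigger for PCP approval, but no schedule or eligibility list contains it, and the enrollment workflow does not show how required approvals are identified and checked before assignment

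*Combined protocol and SAP*

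**What the plan says.** Section 12, under Physical Activity, lists four findings in people being screened that call for PCP approval: a cardiovascular disease (CVD) event more than 6 months earlier, diabetes, peripheral vascular disease (PVD), and a positive Rose Angina Questionnaire. The last two are worded "peripheral vascular disease, or a positive Rose Angina Questionnaire, PCP approval is required". The same section sets the timing. Under Hypoglycemia it says "we will require PCP approval prior to enrolling individuals with diabetes", and under Cardiovascular Events it says that participants with CVD "require approval from their PCP prior to enrolling".

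Section 6 has its own list under Inclusion Criteria, introduced by "Persons with the following conditions are eligible with PCP approval". It contains diabetes, a CVD event more than 6 months ago, and stable CVD or PVD. It does not mention the Rose questionnaire.

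Section 8 describes enrollment. At the waiting-room contact, "Most patients will complete screening and enrollment activities in this initial visit". REDCap assigns the condition "if the would-be participant met all inclusion criteria and reported no exclusion criteria". For people who return for a separate Screening Visit, the order is given as "After consent has been signed, the patient will be randomized and questionnaire data be collected".

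**The concern.** PCP approval is the plan's stated protection for people with cardiovascular risk or diabetes who are about to change diet and activity. If one of its triggers is never assessed, that part of the protection exists only on paper.

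The other triggers raise a question of sequence. If the need for approval comes to light, or approval is refused, after REDCap has assigned a condition, two outcomes remain: the patient takes part without the approval that section 12 requires, or is withdrawn after randomization. The first is a safety matter. The second weakens the as-randomized comparison that section 14 makes primary. Section 12 also states that there is no data safety and monitoring board, so more weight rests on the checks made at entry.

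**Working it through.** No sample size, power or error-rate figure is involved, so the check is a comparison of the relevant places.

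**Step 1. Trace each trigger in section 12 (Physical Activity) through the other sections.**

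| Trigger | Section 6 approval list | Table 3 screener | Diagnosis question (section 8, Demographic) |
|---|---|---|---|
| Diabetes | Listed | Current insulin use only, as an exclusion | Named |
| CVD event over 6 months ago | Listed | Heart attack in the past 12 months only, as an exclusion | Named as heart disease |
| PVD | Listed | Not asked | Not named |
| Positive Rose questionnaire | Not listed | Not asked | Angina symptoms not asked |

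Stable CVD, which section 6 adds, is not asked in Table 3 either. None of the 18 statements in Table 3 refers to PCP approval.

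**Step 2. Look for the Rose questionnaire as a scheduled measure.** Table 4 has no row for it or for angina. The measure descriptions in section 8 do not include it. The row that might be expected to carry it, "Medical History survey", is marked only at 6 and 12 months. Result: 1 of 4 triggers has neither an assessment nor a place in the eligibility criteria.

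**Step 3. Apply the randomization rule.** Assignment requires every inclusion criterion to be met and no exclusion to be reported.
- Diabetes, past CVD event, stable CVD or PVD: PCP approval is itself an inclusion criterion, so the rule covers it by reference. Randomizing such a patient without approval would breach section 6.
- Rose-positive only: section 6 asks for nothing further. If no exclusion applies, the patient satisfies the rule, although section 12 requires approval.

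**Step 4. Establish when the qualifying conditions are known.**
- The Screening Visit text in section 8 reads as consent, then randomization, then questionnaires.
- The Randomization procedure text in the same section makes assignment depend on screening and baseline measures already showing eligibility.
- Table 4 marks the Demographics/Medical row at both Screening and Baseline, and Randomization at Baseline.

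The second and third fit together; the first does not. Whichever order is intended, no text says when approval is requested, who records it, or what confirms it before REDCap assigns.

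**The case against.** The strongest reply concerns the conditions listed in section 6. A reader might infer that the randomization rule has no approval condition at all, so that patients with diabetes or CVD may be randomized without one. The documents do not support that. The rule demands that all inclusion criteria be met, approval is among them, and sections 8 and 10 both require that the patient remains eligible. This part of the reply stands in full.

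It can also be said that the PCP is not absent from screening. Section 12 promises that safety to participate is judged at screening together with the PCP, and that a Health Safety Officer reviews medical eligibility as needed. Recruitment happens in the PCP's own clinic and many patients are called to their appointment during it, so same-visit enrollment does not rule out prior approval. A form or data-entry hold could properly sit in the fieldwork manual described in section 9. This stands as far as it goes: the form of the record is operational detail. It does not supply the missing step, because none of these texts says how a patient needing approval is recognized before assignment. The PCP contact described for enrollment in section 3 and for the screening visit in section 11 is encouragement to take part.

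Finally, section 8 allows questionnaires to be added, section 6 excludes unstable angina, and Table 3 removes people with a condition limiting diet or exercise. These reduce the exposure. They do not schedule the Rose questionnaire, which section 12 treats as a present requirement.

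**Conclusion.** The point holds in two parts of unequal weight.

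1. The Rose trigger is wrong as written. Section 12 requires it, while section 6, Table 3, Table 4 and the measure descriptions omit it. A Rose-positive patient with no other listed condition would go unidentified and could be randomized in conformity with section 6 but contrary to section 12. This rests on the text alone.
2. For diabetes, past CVD events, and stable CVD or PVD, the rule is in place but its operation is not shown. Table 3 does not pick up diabetes without insulin, stable CVD or PVD, the diagnosis question does not name PVD, and section 8 is inconsistent on order.

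The number of patients affected cannot be derived. The documents give neither the share who would be Rose-positive nor the share with the listed conditions. One might assume a comorbidity prevalence and apply it to the 261 participants, but the result would mainly count people whose approval section 6 already requires, and so would not measure the first gap.

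This is a consistency defect in a safety check. It should be corrected, but it is not a flaw that by itself puts the trial's conclusions in doubt.

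**What to change.** Reconcile the Physical Activity text of section 12 with section 6 and Table 4. Whether the Rose trigger stays is for the investigators and the Health Safety Officer to decide. If it stays, add it to the section 6 approval list and schedule it at screening, before randomization. If it does not, remove it from section 12.

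Reconcile the Screening Visit and Randomization procedure texts in section 8, so that the conditions requiring approval are ascertained, and approval status confirmed, before REDCap assigns a condition. Make sure that each condition in the section 6 list, including PVD, is asked about at that stage. How the confirmation is recorded can be left to the fieldwork manual.

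The cost is wording in sections 6, 8 and 12, one added screening instrument if the Rose trigger is kept, and possibly a short delay to randomization for patients awaiting approval. No new clinical rule is introduced.

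### Table 9 gives an average SBP of 70 or less the slowest PCP advice of any alert row (2 months), although section 12 names hypotension as a risk of the intervention

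*Combined protocol and SAP*

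**What the plan says.** Section 12, Alert Values (Table 9, called Table 8 in the sentence that introduces it), has three blood pressure rows and two PHQ-9 rows, each with advice to be given to the participant in clinic. The blood pressure rows use the average reading. Level 3, SBP of 70 or less or DBP of 50 or less, carries the instruction "Advise to follow-up with PCP within 2 months". No reason is given for this interval.

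On the risk itself, the subsection on symptomatic hypotension states that "weight loss interventions have the potential to increase the risk of hypotension", with reference to those taking antihypertensive drugs. It leaves changes to blood pressure treatment with the participant's PCP.

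Several safeguards sit around the table, all in section 12:

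- The opening of the section says "the staff were prepared to address immediately items meeting the criteria for" alert values.
- The lead-in to Table 9 says "In general, the participant, safety officer, and PCP will be notified".
- For abnormal physical measurements such as blood pressure, "we referred the patient to her primary care physician and follow-up to make sure that she completed the referral".
- The Health Safety Officer role has back-up "to provide 24/7 medical safety coverage for the duration of the study".
- Participants are taught the symptoms of hypotension and urged to call the PCP if they occur, and "staff contact will notify PCP of participants who develop symptomatic hypotension while on anti-hypertensive medications".
- Events may be reported at coaching contacts, and the study team reviews adverse events weekly.

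**The concern.** The windows should run roughly in order of urgency. For high pressure they do: the more extreme reading gets the shorter window. The low-pressure row breaks the pattern. A participant with an average SBP of 70 is told that a PCP visit can wait twice as long as it can for a participant with an SBP of 140.

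This is hard to square with the rest of the protocol. Hypotension is listed as a risk of the intervention. Section 4 admits patients with uncomplicated hypertension, some of whom can be expected to take antihypertensives. The abstract expects MyPlate to lower systolic pressure, and Table 6 sets a 1500 mg sodium target for that arm. Because the PCP controls the regimen, the PCP visit is the route by which a drug dose would be reduced, and that is the visit the table lets slide.

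What is at stake is participant safety: the advice that trained data collectors give after a very low reading.

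**Working it through.** No power, alpha or sample-size figure is involved. The check is to order the windows in Table 9 and then ask whether any other text overrides the slowest one.

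**Step 1. The five windows** (Table 9; 1 month taken as about 30 days, 2 months as about 60):

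| Row | Trigger | Advised PCP window | Days |
|---|---|---|---|
| BP Level 1 | SBP ≥ 180 or DBP ≥ 110 | 1 week | 7 |
| BP Level 2 | SBP ≥ 140 or DBP ≥ 90 | 1 month | 30 |
| BP Level 3 | SBP ≤ 70 or DBP ≤ 50 | 2 months | 60 |
| PHQ-9, lower | 16 to 20 | 1 month* | 30 |
| PHQ-9, upper | 21 or more | 1 week* | 7 |

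*PCP or mental health care provider.

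In order: 7, 7, 30, 30, 60. Level 3 is the single longest.

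**Step 2. Ratios.** Level 2 and Level 1 overlap as written. An SBP of 180 or more goes to Level 1, so the 1-month systolic comparator is SBP 140–179.

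- Level 3 against SBP 140–179: 60 / 30 = 2.0.
- Level 3 against SBP 180 or more: 60 / 7 = 8.6.

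**Step 3. Does other text shorten the Level 3 window?**

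- *Immediate attention.* It covers every item in the table, so it covers Level 3. The action is not described, and it does not alter what the participant is told.
- *Notification of the safety officer and PCP.* It is stated as the general practice, with no time limit.
- *Referral tracking.* It checks that the referral was completed, but sets no date for it.
- *24/7 cover.* It provides capacity. Table 9 does not say that a Level 3 reading triggers a call.
- *Hypotension rules.* Advice to call the PCP depends on symptoms. Staff notification depends on symptoms and on antihypertensive use. An asymptomatic participant meets neither condition.
- *Weekly adverse-event review.* It sets no deadline for PCP evaluation.

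None of these replaces the 2-month advice. For an asymptomatic participant, Table 9 is the only place that states an interval to PCP review.

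**The case against.** The strongest reply is that the 2 months is advice in a column headed for participant notification, not the clinical response time. Section 12 says alert values are addressed at once, and Level 3 is one of them. The safety officer and PCP are in general told, the referral is followed up, and cover is continuous. Symptomatic hypotension has its own pathway that does not wait for Table 9. Most follow-up measurements are taken at the clinic, where help is close. The row will rarely fire, and the documents contain no evidence on the clinically correct interval.

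Most of this stands, and it limits the consequence. It does not remove the point. A participant who feels well is still told that 2 months is acceptable, and nothing on the page corrects that. Nor does the comparison need an outside guideline: the protocol's own windows for high pressure are shorter.

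Three stronger readings are tempting and should not be drawn.

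- A reader might infer that a very low reading would go unattended for 2 months. The safeguards above apply to this row and contradict that.
- A reader might infer from Table 7, which places all 11 sessions in months 1 to 3, that nobody is in contact after a low reading at 6 months. Section 11 describes coaching calls to both arms throughout the study and allows make-up sessions, so this does not follow. The gap between the 6-month and 12-month blood pressure measurements is the same for every alert row and says nothing particular about Level 3.
- A reader might infer that 2 months is also wrong for an isolated, asymptomatic DBP of 50 or less. The documents do not show that.

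**Conclusion.** The point holds for an average SBP of 70 or less and should be fixed. Table 9 gives that reading the slowest advice of its five rows, 2.0 times the window for SBP 140–179 and about 8.6 times that for SBP 180 or more. No rationale is offered, and the same section names hypotension as an intervention risk. Existing safeguards reduce the likely harm but do not change the advice, which matters most for a participant without symptoms.

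The ordering of the windows is certain from the table. That an SBP of 70 or less should not be slower than 140–179 is a clinical judgement, though one consistent with the protocol's own risk statement. The number of participants affected is not given; I assume it is small. No efficacy endpoint, sample size or analysis is touched.

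**What to change.** Split Level 3 in Table 9, keeping the average blood pressure that the table already uses:

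- **(a) Average SBP of 70 or less:** contact the Health Safety Officer the same day, and advise PCP follow-up no later than the 1-week window already set for Level 1.
- **(b) DBP of 50 or less with average SBP above 70:** if the participant is symptomatic or on antihypertensives, handle as in (a). Otherwise use an interval set by the Health Safety Officer.

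The trigger should stay on the average and not require both readings to be low. Readings of 66 and 74 average (66 + 74) / 2 = 70 and meet Level 3 now, but a both-readings rule would miss them. The intervals are clinical proposals that do not come from the documents, and the Health Safety Officer should confirm them.

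The cost is a wording change to Table 9 and the fieldwork manual and a short staff re-briefing. The downside is a few extra safety-officer contacts for readings that prove benign. Row (a) uses cover that the protocol already provides.
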